4 STUDY DESIGN

4.1 Overall Design

4.1.1 Master Protocol Structure

The overall study design will include a Master Protocol with Substudies. Information relating to the overall study, including study objectives, rationale, master inclusion and exclusion criteria, safety assessments, and AE reporting can be found in the Master Protocol (ie, Sections 1-9). In addition to the Master Protocol, individual "Substudies" will contain elements specific to each individual Substudy. Substudy 1 as described below, includes both a dose escalation and 2 expansions for monotherapy. The content of additional Substudies has not yet been defined and will be further added based on emerging supportive preclinical data.

The information in this Master Protocol cannot be superseded by information in the Substudies. Any change to the study master elements (ie, this Master Protocol) or Substudies will be submitted to Regulatory Authorities and ethics committees according to the local legislation/requirements.

Study drug-specific information including doses and justifications, toxicity management, dose modifications and concomitant medications can be found in the relevant Substudy(ies).

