5 STUDY POPULATION

All criteria and considerations listed in this section are for the master study design and apply to all Substudies of the study. Additional Substudy-specific criteria and considerations are listed in the study population section of the relevant Substudy.

Prospective approval of protocol deviations to recruitment and enrolment criteria, also known as protocol waivers or exemptions, is not permitted.

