	Total bilirubin	≤ 1.5 × ULN in the absence of Gilbert's syndrome	
Hepatic		≤ 3 × ULN if the participant has Gilbert's syndrome	
	Alanine transaminase and aspartate transaminase	≤3.0 × ULN. ≤5 × ULN in case of liver metastasis.	
Renal	Calculated creatinine clearance ^a	≥ 50 mL/minute² (≥ 45 mL/minute² for urothelial carcinoma participants).	

As determined by Cockcroft-Gault (using actual body weight):

Males:

Creatinine CL = Weight (kg) \times (140 – Age) (mL/min) 72 x Serum creatinine (mg/dL) Females:

Weight (kg) x (140 – Age) x 0.85 Creatinine CL = 72 x Serum creatinine (mg/dL) (mL/min)

Abbreviations: ULN = upper limit of normal.

5.2 **Exclusion Criteria**

The below are the master exclusion criteria for all Substudies of the study; all participants must meet the criteria described in the relevant Substudy in addition to those described below. Where Substudy-specific criteria are more stringent than master study criteria, the Substudy-specific criteria take precedent.

Participants are excluded from the study if any of the following criteria apply:

Medical Conditions

1. Participants with a history of thromboembolic events within 6 months of Cycle 1 Day 1 unless they received adequate treatment. Please discuss with the Study Physician to determine study eligibility.

- 2. Unresolved toxicities of ≥ Grade 2 (CTCAE v5.0) from prior therapy (excluding vitiligo, alopecia, endocrine disorders that are controlled with replacement hormone therapy, asymptomatic laboratory abnormalities). Participants with ≥ Grade 2 neuropathy will be evaluated on a case-by-case basis after consultation with the Study Physician.
- 3. Symptomatic CNS metastasis or leptomeningeal disease.
- 4. Ongoing or an active infection, including tuberculosis (clinical evaluation that includes clinical history, physical examination and radiographic findings, and tuberculosis testing in line with local practice), hepatitis B (known positive HBsAg result), hepatitis C, or HIV (positive HIV 1/2 antibodies).
- 5. Participants with a past or resolved HBV infection (defined as the presence of anti-HBc and absence of HBsAg) are eligible. Participants positive for HCV antibody are eligible only if polymerase chain reaction is negative for HCV RNA.

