8.2.5 Clinical Safety Laboratory Assessments

Blood and urine samples for determination of clinical chemistry, haematology, coagulation, virology, and urinalysis will be taken at the timepoints indicated in the respective Substudy SoA.

Additional safety samples may be collected if clinically indicated at the discretion of the Investigator. The date of collection and results (values, units, and reference ranges) will be recorded on the appropriate eCRF.

The analysis of safety samples will be performed at a local laboratory at or near to the Investigator site. Sample tubes and sample sizes may vary depending on laboratory method used and routine practice at the site.

For all participants, results of safety laboratory testing (haematology, coagulation and clinical chemistry at a minimum) must be available within 24 hours prior to dosing and must be reviewed by the Investigator prior to administration of AZD8853. Samples can be collected the day before AZD8853 administration. If clinically indicated, additional clinical laboratory tests and evaluations may be performed by the Investigator and these need to be entered into the eCRF.

The laboratory variables to be measured for haematology, clinical chemistry, urinalysis, coagulation, virology, and pregnancy testing are listed in Table 10.

Table 10 Laboratory Safety Variables

Haematology (whole blood)		Clinical Chemistry (serum or plasma)		
B-Hb		S/P-Creatinine	S/P-Chloride	
B-WBC count with differential		S/P-Bilirubin total	S/P-Magnesium	
B-Platelet count		S/P-Direct and indirect bilirubin	S/P-Phosphorus	
B-Haematocrit		S/P-Alkaline phosphatase	S/P-Cholesterol	
B-Absolute neutrophil co	ount	S/P-Aspartate transaminase	S/P-Amylase	
B-Absolute lymphocyte	count	S/P-Alanine transaminase	S/P-Lipase	
		S/P-Albumin	S/P-TSH	
Urinalysis (dipstick)		S/P-Free T3	S/P-Free T4	
Colour and appearance		S/P-Potassium	S/P-Bicarbonate	
U- Hb/Erythrocytes/Blood	U- Protein/Albumin	S/P-Calcium, total	S/P-Total protein	
U-Glucose	U-pH	S/P-Sodium	S/P-Blood urea nitrogen	
U-Specific gravity	U-Ketones	S/P-Creatine phosphokinase	S/P-Glucose (fasting preferred)	
U-Microscopy including WBC/high-power field, RBC/high-power field ^a		S/P-HbA1c	S/P-Triglycerides	
		S/P-lactate dehydrogenase		
Coagulation		I		
INR PT		aPTT, absolute or relative	D-Dimer	Fibrinogen
Virology				,
Hepatitis B virus core antibodies		Hepatitis A serology		
Hepatitis C serology		HIV-1 and 2 antibodies		
Hepatitis B virus surface antigen				

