- Participants with active hepatitis A, active hepatitis B, or active hepatitis C are excluded; however, participants who have chronic hepatitis B or hepatitis C receiving suppressive antiviral therapy are allowed to be enrolled if ALT is normal and viral load is controlled. Controlled hepatitis B viral load is defined as serum hepatitis B virus DNA < 2000 IU/mL by PCR. Controlled hepatitis C viral load is defined as undetectable hepatitis C RNA by PCR either spontaneously or in response to a successful prior course of anti-hepatitis C therapy. NOTE: Participants with controlled hepatitis B viral load must remain on antiviral therapy, per institutional practice, to ensure adequate viral suppression during the study treatment and follow-up period.
- Fresh paired biopsy samples will be taken as specified in all mandatory paired biopsy cohorts in Parts B but are optional for all other participants. CCI

 If they are taken during screening they will not need to be taken for Cycle 1

 Day 1 pre-dose.
- Whole body PET imaging to occur before the initial dosing of study intervention (≤ 14 day) on Cycle 1 Day 1. Imaging to be done only after the participant's eligibility for the study has been confirmed. PET imaging must be before pre-treatment biopsy. CD8+ PET Tracer [89Zirconium (Zr)-deferoxamine (Df)-crefmirlimab] to be ordered at least 72 hours before administration and PET imaging appointments should be booked accordingly. Tracer to be administered preferably 24 (±3) hours but not more than 72 hours prior to whole body PET imaging. The duration between administration of the tracer and the PET scan should be the same at screening and at Day 29. If a participant holds or discontinues study treatment prior to Day 29, if able, the participant should still perform the PET scan as scheduled.

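### The Table 12 virology footnote lets controlled, HBsAg-positive chronic hepatitis B enrol, although master exclusion 4 bars it and governs

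*Protocol*

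**What the plan says.** Three sets of text bear on whether someone with treated chronic hepatitis B may enter Substudy 1.

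- **Table 12 footnote (Protocol 10.1.2, screening virology).** It first excludes active hepatitis A, B or C. It then says that people with "chronic hepatitis B or hepatitis C receiving suppressive antiviral therapy are allowed to be enrolled if ALT is normal and viral load is controlled". The threshold follows: "Controlled hepatitis B viral load is defined as serum hepatitis B virus DNA < 2000 IU/mL by PCR". A note adds that those with controlled hepatitis B must stay on antivirals during treatment and follow-up. HBsAg is not mentioned.
- **Master exclusion criteria (Protocol 5.2).** Item 4 excludes ongoing or active infection, including "hepatitis B (known positive HBsAg result), hepatitis C, or HIV (positive HIV 1/2 antibodies"). Item 5 adds: "Participants with a past or resolved HBV infection (defined as the presence of anti-HBc and absence of HBsAg) are eligible".
- **Rules of precedence.** Protocol 4.1.1: "The information in this Master Protocol cannot be superseded by information in the Substudies". The introduction to Section 5.2, repeating Section 5.1: "Where Substudy-specific criteria are more stringent than master study criteria, the Substudy-specific criteria take precedent". Section 5 says that prospective approval of deviations from entry criteria, "also known as protocol waivers or exemptions, is not permitted".

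The Substudy 1 exclusions in Section 10.5.2 apply on top of those in Section 5.2.

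**The concern.** A site screening a participant with treated hepatitis B meets two instructions with opposite answers. The permissive one is attached to the screening virology row, where staff look when the result arrives. The eligibility row of the same table cites Sections 10.5.1 and 10.5.2, so exclusion 4 is reached only through the cross-reference in Section 10.5.2. A site could enrol in good faith someone whom the governing criteria bar.

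This is the first study of AZD8853 in humans. The DLT definition (Protocol 10.6.8) includes a combined rise in transaminases and bilirubin that counts only if nothing but the study drug explains it. Appendix E uses the same condition for Hy's Law and names viral hepatitis as a possible alternative cause. Known hepatitis B makes that judgement harder. Escalation decisions can rest on 3 to 9 DLT-evaluable participants per dose (Protocol 10.6.6.1.3). One event reclassified either way moves the observed DLT rate by 1/3 = 33 percentage points with 3 participants, or 1/9 = 11 with 9.

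Enrolment under the footnote would also breach a core entry criterion. SAP 3.3.5 lists that type among the important deviations that may influence analysis.

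**Working it through.** No calculation applies. The check is to put one participant through both texts and then apply the protocol's rules of precedence.

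**Test case (illustrative).** Chronic hepatitis B, HBsAg positive, on suppressive antivirals, normal ALT, HBV DNA 500 IU/mL.

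| Feature | Table 12 footnote | Section 5.2, items 4 and 5 |
|---|---|---|
| HBsAg positive | No condition set | Excluded by item 4; item 5 requires HBsAg to be absent |
| On antivirals | Required | Gives no exception |
| ALT normal | Required | Gives no exception |
| HBV DNA 500 IU/mL, below 2000 | Counts as controlled | Gives no exception |
| Result | May enrol | May not enrol |

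**Would the HBsAg result be known?** Yes. The Table 10 virology list includes "Hepatitis B virus surface antigen", and Table 12 schedules virology at screening, before dosing.

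**Does item 5 admit the participant?** No. It covers past or resolved infection and defines that by absence of HBsAg. The footnote describes infection that is still being treated, that may still be viraemic below the threshold, and that needs continued antivirals.

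**Which text prevails?**
1. The footnote is Substudy text, and Section 4.1.1 does not let Substudy text displace master text.
2. Section 5.2 lets a Substudy criterion take over only when it is stricter. The footnote is more lenient.
3. Section 5 forbids waivers, so the footnote cannot serve as one.
4. Section 10.5.2 adds exclusions to those in Section 5.2. Part of it is redacted, but the redacted items are themselves exclusions and could only restrict entry further.
5. Neither the amendment summary nor Global Addendum 2 deals with the point.

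Exclusion 4 therefore governs.

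**Extent of the conflict.** It is confined to hepatitis B. For hepatitis C the footnote defines control as undetectable RNA, which agrees with the PCR-negative condition in item 5. Chronic hepatitis B that fails any of the footnote's conditions does not qualify under its allowance, so the two texts do not clash there.

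**Supporting test.** The footnote's allowance depends on HBV DNA, which Table 10 does not list. HBV DNA appears only in the Appendix E list for working up liver abnormalities.

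**The case against.** The best contrary reading is that exclusion 4 concerns active disease and the footnote merely explains what counts as active. The footnote does begin by excluding active hepatitis B, and it never uses the term HBsAg. This reading fails: exclusion 4 covers ongoing as well as active infection, identifies hepatitis B by a positive HBsAg, and is followed by an item that makes HBsAg absence part of the eligible state.

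Other points carry some weight.

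- The protocol already resolves the conflict, and a site that works through Section 10.5.2 to Section 5.2 will exclude the participant. That is true. It limits the harm but leaves a misleading instruction in the screening schedule.
- The missing HBV DNA test is weak evidence by itself. Item 5 relies on HCV RNA, which Table 10 also omits, and Section 8 and Section 8.2.5 allow routine-care results and extra samples. This stands, so the point is secondary and the contradiction does not depend on it.
- SAP 3.3.5 says that such deviations may be included and leaves the definitions to the Protocol Deviation Assessment Plan, which is not available here. Classification as an important deviation is likely but not established.
- The liver risk is reduced. The footnote requires normal ALT, whereas Table 6 admits ALT up to 3 × ULN, or 5 × ULN with liver metastases. Antivirals continue, and Appendix E provides for viral hepatitis testing. Attribution is still harder when hepatitis B is known to be present.
- The documents do not show which text the sponsor intended. That affects the choice of correction, not the existence of the conflict.

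**Conclusion.** The concern holds. As written, the footnote permits enrolment of a participant whom exclusion 4 bars, and the protocol's own rules make exclusion 4 the governing text.

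The affected group is HBsAg-positive participants on suppressive antivirals with normal ALT and HBV DNA below 2000 IU/mL. Their expected number cannot be derived from the documents. No estimate, sample size or decision rule changes. SAP 3.3.5 keeps participants with deviations in the analysis sets unless the Protocol Deviation Assessment Plan says otherwise, so the consequence is for eligibility, safety and attribution of liver events.

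The conclusion rests on the visible text and on reading the redacted items in Section 10.5.2 as further exclusions, as their heading states. The correction should be made, but this is a contained inconsistency and not a flaw in the design.

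**What to change.** At the next amendment, delete from the Table 12 footnote the allowance for chronic hepatitis B, its viral-load definition and the note on continuing antivirals. Replace them with a reference to Section 5.2, items 4 and 5. The hepatitis C eligibility text needs no change. The cost is one footnote, and Global Addendum 2 already expects a further global amendment.

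If the sponsor does intend to admit controlled chronic hepatitis B, the change belongs in the master criteria: amend Section 5.2, items 4 and 5, to carry the footnote's conditions, and add HBV DNA to the screening virology in Table 10. That costs two criteria and one laboratory test.

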8.2 Safety Assessments

Planned timepoints for all safety assessments are provided in the respective Substudy SoA and are detailed below.

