10.1.2 Schedule of Activities

 Table 12
 Schedule of Activities - Screening

Study Period	Screening	
Visit Number	V1	Details in Section
Procedure/Study Day	Days -28 to -1 a	
Screening informed consent (Main Study)	X	10.5, Appendix A 3
Assignment of participant identification number (PID / E-Code) in IRT	X	6.3
Metformin Use History, including date of last dose	X	5.2, Table 8
CCI	X	8.8
Confirm eligibility for enrolment in Main Study	X	10.5.1; 10.5.2
Medical and Disease History		•
Demographics	X	8.2.1
Medical/surgical history, including smoking history	X	8.2.1
Disease history and characteristics, including biomarkers and CCI	X	8.2.1
Prior cancer treatment, including surgeries, radiotherapy, and systemic therapy	X	8.2.1
Disease Assessments		•
Disease assessment by RECIST v1.1 and SMI assessment ^b	X °	10.8.1
CT or MRI, Brain (Required for NSCLC participants, participants with known brain metastasis, and as clinically indicated for other participants)	Χ°	10.8.1
Study Procedures and Examinations		•
Physical examination, including assessment of appetite	X	8.2.1
ECOG performance status	X	8.2.2
Vital signs, including weight	X	8.2.3
Height	X	8.2.1
Local 12-lead ECG (triplicate)	X	8.2.4
Assessment of AEs/SAEs	X	8.3

Study Period	Screening	
Visit Number	V1	Details in Section
Procedure/Study Day	Days -28 to -1 a	
Concomitant medications	X	6.5
Safety Laboratories		-
Clinical chemistry	X	8.2.5
HbA1c	X	8.2.5
Thyroid function tests (TSH, free T4, free T3)	X	8.2.5
Haematology	X	8.2.5
Urinalysis	X	8.2.5
Serum pregnancy test (WOCBP)	X	8.2.5
Coagulation parameters (PT/aPTT/INR/d-dimer/fibrinogen)	X	8.2.5
Virology (Hepatitis A, B, and C, HIV-1 and HIV-2) ^d	X	8.2.5
Biomarker Evaluations		
CCI	X	10.8.6.2
Part A/C: CCI e	X	10.8.6.1.2
Part B: Mandatory paired biopsy ^e	X	10.8.6.1.1
Serum for GDF15 target engagement	X	10.8.5.3.1
Whole blood for CCI (refrigerated)	X	10.8.6.4
Whole blood for flow cytometry	X	10.8.6.5
Whole blood for CCI	X	10.8.6.3
CCI	X	10.8.6.7
CCI	X	10.8.6.7
Plasma for circulating tumour DNA	X	10.8.6.6
Part B only: CD8+ PET (select and validated sites only)	·	
CD8+ PET tracer administration	X f	Appendix I
Whole body PET scan	X f	Appendix I

The screening period may last no longer than 28 days from Cycle 1 Day 1.

- b To include CT or MRI slices through T12 and L3.
- ^c Previous scans for baseline disease and brain imaging that were performed within 4 weeks of dosing and meet the protocol requirements do not need to be repeated.

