Abbreviations: AE = adverse event; ALT = alanine aminotransferase; aPTT = activated partial thromboplastin time; CD8 = cluster of differentiation 8; CT = computed tomography; DNA = deoxyribonucleic acid; ECG = electrocardiogram; ECOG = Eastern Cooperative Oncology Group; GDF15 = growth differentiation factor 15; HbA1c = haemoglobin A1c; HIV = human immunodeficiency virus; IRT = interactive response technology system; INR = international normalised ratio; MRI = magnetic resonance imaging; NSCLC = non-small-cell lung carcinoma; CCl cell; PET = positron emission tomography; PT = prothrombin time; PID = participant identification number; RECIST = response evaluation criteria in solid tumours; RNA = ribonucleic acid; SAE = serious adverse event; T3 = triiodothyronine; T4 = thyroxine; TSH = thyroid-stimulating hormone; V = visit; WOCBP = woman of childbearing potential.

Table 13 Schedule of Activities – Study Visits

Visit Number	,	V2	V3	V4	V5	V6	V7	V8	V9	V10	V11	V12	V13-Vn	Details in Section
Procedure/Study Day	D1 Pre- Dose	D1 Post- Dose	D2	D8	D15	D22	D29	D36	D43	D64	D85	D106	D127+ Q3W	
Week	1	1	1	2	3	4	5	6	7	10	13	16	19+	
Cycle Number and Cycle Day ^a	C1D1	C1D1	C1D2	C1D8 (±1D)	C1D15 (±1D)	C2D1 (±1D)	C2D8 (±1D)	C2 D15 (±1D)	C3D1 (±3D)	C4D1 (±3D)	C5D1 (±3D)	C6D1 (±3D)	C7D1-CnD1 (±3D)	
Eligibility	Į.	1			1	I .	1			Į.	ll .	I .	II.	1
Confirm eligibility for enrolment in Main Study	X													10.5.1; 10.5.2
Study Procedures	and Exar	ninations			•									
Physical examination, including appetite assessment	X			X	X	X	X °	X °	X	X	X	X	X	8.2.1
Local 12-lead ECG	X	X				X			X				X Q12W	10.8.2.1 Table 17
Vital signs, including body weight	X	X d		X	X	X	X °	Χ°	X	X	X	X	X	8.2.3
ECOG Performance Status	X			X	X	X	X °	X °	X	X	X	X	X	8.2.2
Assessment of AEs/SAEs	X	X	X	X	X	X	X c	X c	X	X	X	X	X	8.3

Visit Number	•	V2	V3	V4	V5	V6	V7	V8	V9	V10	V11	V12	V13-Vn	Details in Section
Procedure/Study Day	D1 Pre- Dose	D1 Post- Dose	D2	D8	D15	D22	D29	D36	D43	D64	D85	D106	D127+ Q3W	
Week	1	1	1	2	3	4	5	6	7	10	13	16	19+	
Cycle Number and Cycle Day ^a	C1D1	C1D1	C1D2	C1D8 (±1D)	C1D15 (±1D)	C2D1 (±1D)	C2D8 (±1D)	C2 D15 (±1D)	C3D1 (±3D)	C4D1 (±3D)	C5D1 (±3D)	C6D1 (±3D)	C7D1-CnD1 (±3D)	
Concomitant medications	X		X	X	X	X	X c	X c	X	X	X	X	X	6.5
Disease Assessmen	ts													
Disease assessment by RECIST v1.1 and SMI assessment °									X D1-D7			X ^f W15 D1-D7	W24±6D then Q9W±6D until W52, then Q12W±6D	10.8.1

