Week	1	1	1	2	3	4	5	6	7	10	13	16	19+	
Cycle Number and Cycle Day ^a	C1D1	C1D1	C1D2	C1D8 (±1D)	C1D15 (±1D)	C2D1 (±1D)	C2D8 (±1D)	C2 D15 (±1D)	C3D1 (±3D)	C4D1 (±3D)	C5D1 (±3D)	C6D1 (±3D)	C7D1-CnD1 (±3D)	
Part C: AZD8853 PK	X	X				X			X	X	X	X		10.8.5.1; Table 18
Study Treatment A	dministr	ation												
AZD8853 administration (Q3W)	X					X			X	X	X	X	Q3W	6.1
Part B only: CD8+	PET (sel	ect and v	alidated s	ites only)										
CD8+ PET Tracer Administration							X °							Appendix I
Whole body PET scan							X °							Appendix I

Any timing of safety assessment visit is relative to the day of most recent dosing (Day 1 of the latest cycle).

- c For Part A only.
- d Weight on Day 1 post-dose is not needed.
- To include CT or MRI slices through T12 and L3. Any timing of tumour assessment visit is relative to Cycle 1 Day 1.
- f Disease assessment should be performed on the week prior to next assessment cycle, always prior to dosing.
- g All collections must be pre-dose unless specified otherwise.
- h Sample can be taken at any point during study.
- Free T4 and T3 measured if TSH is abnormal or if clinical suspicion of an AE related to the endocrine system.
- A urine or serum pregnancy test is acceptable; if urine test is equivocal or positive then serum β-hCG testing should be performed for confirmation.
- Required for participants with a history of hepatitis B or hepatitis C.

If screening assessments have been performed within the 72 hours prior to Day 1, then the assessment does not need to be performed pre-dose on Day 1. All safety laboratory results must be reviewed by the Investigator or physician designee prior to administration of the scheduled dose of study intervention. Pregnancy testing for WOCBP is required on all days of dosing.

- Fresh paired biopsy samples will be taken as specified in all mandatory paired biopsy cohorts in Parts B but are optional for all other participants. If they are taken during screening they will not need to be taken for Cycle 1 Day 1 pre-dose.
- The second paired biopsy sample should be collected on Cycle 2 Day 8 (# days relative to Cycle 2 Day 8). For participants who are in the CD8+ PET cohort, the first and second biopsy should be taken within hours after the first and second CD8+ PET scan, respectively. This second biopsy must still be collected if not done within the time windows described.
- To be taken at time of second paired biopsy.

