- Whole body PET imaging to occur before the initial dosing of study intervention (≤ 14 day) on Cycle 1 Day 1. Imaging to be done only after the participant's eligibility for the study has been confirmed. PET imaging must be before pre-treatment biopsy. CD8+ PET Tracer [89Zirconium (Zr)-deferoxamine (Df)-crefmirlimab] to be ordered at least 72 hours before administration and PET imaging appointments should be booked accordingly. Tracer to be administered preferably 24 (±3) hours but not more than 72 hours prior to whole body PET imaging. The duration between administration of the tracer and the PET scan should be the same at screening and at Day 29. If a participant holds or discontinues treatment prior to Day 29, if able, the participant should still have the PET scan as scheduled.

Abbreviations: ADA = antidrug antibody; AE = adverse event; CR = complete response; CT= computed tomography; D = Day; DNA= deoxyribonucleic acid; ECG = electrocardiogram; ECOG = eastern cooperative oncology group; EOT = end of treatment; GDF15 = growth differentiation factor 15; HbA1c = haemoglobin A1c; MRI = magnetic resonance imaging; n = visit number; NSCLC = non-small-cell lung cancer; CC ; PK = pharmacokinetic; PR = partial response; Q3W = every 3 weeks; Q6W = every 6 weeks; Q9W = every 9 weeks; Q12W = every 12 weeks; Q26W = every 26 weeks; RNA = ribonucleic acid; RECIST = response evaluation criteria in solid tumours; SAE = serious adverse event; SD = stable disease; T3 = triiodothyronine; T4 = thyroxine; TSH = thyroid-stimulating hormone; V = visit; WOCBP = woman of childbearing potential.

Table 14 Schedule of Activities – End of Treatment

Study Period	EOT	Follow-u	p Post EOT	LTFU	Details in
Procedure/Study Day		Day 30 (± 7 days)	Day 90 (± 7 days)	Q12W Post Day 90 Visit	Section
		Post EOT	Post Last Dose		
Study Procedures and Examinations			•		
Physical examination, including appetite assessment	X	X	X		8.2.1
ECOG performance status	X	X	X		8.2.2
Local 12-lead ECG (triplicate)	X				8.2.4
Vital signs, including body weight	X	X	X		8.2.3
Assessment of AEs/SAEs	X	X	X		8.3
Concomitant medications	X	X	X		6.5
Disease Assessments				1	
Disease assessment by RECIST v1.1 and SMI assessment ^a	X b		X c	Х°	10.8.1
CT or MRI, brain (Required for participants with known brain metastasis and as clinically indicated for other participants)	X b		X °	X °	10.8.1
Safety Laboratories			1	1	
Clinical chemistry	X	X			8.2.5
Haematology	X	X			8.2.5
HbA1c	X	X			8.2.5

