10.8.6.1.1 Mandatory Fresh Paired Biopsies

Up to 40 participants in Part B will be required to provide tumour samples. These participants will be required (mandatory) to undergo a tumour biopsy pre-treatment and during treatment as described below.

- Cycle 1 Day 1 (\leq 14 days, must be before the initial dosing of study intervention)
- Cycle 2 Day 8 (± 5 days, must be after CD8+ PET imaging if participant is in the CD8+ PET cohort).
- Informed consent must be obtained from any participant who agrees to provide tissue for mandatory tumour tissue sample testing.

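### Table 13 gives Part B no scheduled AE/SAE or concomitant-medication check at Visit 7 (Day 29), around the mandatory second biopsy and, in the PET cohort, the tracer infusion

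*Protocol*

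**What the plan says.** Table 13 has a row headed "Assessment of AEs/SAEs" and a row for concomitant medications. Both have unrestricted marks at Visit 6 (C2D1, Day 22) and Visit 9 (C3D1, Day 43). At Visit 7 (C2D8, Day 29) and Visit 8 (C2D15, Day 36) both carry a legible c, and the footnote reads "c For Part A only".

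The Visit 7 column also holds the on-treatment CD8+ PET tracer and scan, which are for Part B only, and the Part B mandatory second biopsy. Section 10.8.6.1.1 times that biopsy as "Cycle 2 Day 8 (± 5 days, must be after CD8+ PET imaging if participant is in the CD8+ PET cohort". The footnote on the Visit 7 research bloods says "To be taken at time of second paired biopsy". For the tracer, the PET footnote says "Tracer to be administered preferably 24 (±3) hours but not more than 72 hours prior to whole body PET imaging".

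Appendix I 6 lists anaphylaxis and hypotension among the tracer's potential risks. It relies on Sections 8.2 and 8.3 for safety monitoring in the PET part. Section 8.2 then says "Planned timepoints for all safety assessments are provided in the respective Substudy SoA and are detailed below".

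**The concern.** Appendix I 6 relies on Section 8.2, Section 8.2 relies on the schedule, and at Visit 7 the schedule drops the Part B check. Participants come in around this time for an invasive procedure, and some also receive an investigational radiolabelled agent, yet nothing in Table 13 prompts the site to ask about adverse events or new medication.

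AE incidence is a primary endpoint (Protocol Section 3, Table 4), and Part B safety data contribute to the RP2D (Section 10.4.1). Section 8.3.2 asks for AE start and stop dates and times and for changes in grade. Recall two weeks later makes these details less reliable. It also makes it harder to tell a transient tracer or biopsy effect from an effect of AZD8853. What is at stake is the completeness and timing of non-serious events.

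**Working it through.** The plan gives no figure to reproduce here. The check compares the table cells and takes day differences.

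**Inputs**
- Visit days (Table 13 header): V6 = Day 22 ± 1; V7 = Day 29 ± 1; V8 = Day 36 ± 1; V9 = Day 43 ± 3.
- Second biopsy: C2D8 ± 5 days, up to 40 participants (Section 10.8.6.1.1).
- On-treatment tracer: Day 29 (Appendix I 4), up to about 20 participants (Appendix I 9).

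**Scheduled AE/SAE and medication checks, nominal days**
- Part A: Days 22, 29, 36, 43, so every 7 days.
- Part B: Days 22 and 43, so 43 − 22 = 21 days apart.
- Tracer or biopsy at nominal Day 29 to the next Part B check: 43 − 29 = 14 days.

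**Effect of the visit windows (indicative only)**
- With C2D8 held at Day 29, tracer (Days 28–30) to V9 (Days 40–46): 40 − 30 = 10 to 46 − 28 = 18 days.
- On the same basis, biopsy (Days 24–34) to V9: 40 − 34 = 6 to 46 − 24 = 22 days.
- These ranges are not exact. Table 13 footnote a ties safety-visit timing to the latest dose, and C2D1 has its own ± 1 day. If C2D8 moves by one day while V9 stays anchored at Day 43, the tracer range becomes 40 − 31 = 9 to 46 − 27 = 19 days. The biopsy range becomes 40 − 35 = 5 to 46 − 23 = 23 days. A delayed cycle or a delayed tracer would change them again. The nominal 21 and 14 days are the figures to use.

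**Are participants on site?** Yes. The biopsy is mandatory throughout Part B, and the Visit 7 bloods are drawn with it. In the PET cohort the preferred interval from tracer to scan is 24 − 3 = 21 to 24 + 3 = 27 hours, and the biopsy follows the scan. At that timing the tracer and the biopsy fall on different days, so one question does not cover both.

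**What a Visit 7 prompt changes.** At nominal timing, the 21-day stretch becomes 29 − 22 = 7 days followed by 43 − 29 = 14 days. An event between tracer and biopsy would be asked about on the biopsy day instead of at V9. The interval from biopsy to V9 stays at 14 days.

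**The case against.** **The duty to collect is continuous.** A reader might infer that Part B reactions around Day 29 would go unrecorded. The documents do not support that. AEs and SAEs are collected from consent through follow-up (8.3.1). Events that are volunteered or observed are recorded, and the open question at V9 reaches back to the last time of asking (8.3.4). All medication received must be recorded (6.5), and SAEs go to the sponsor within 24 hours (8.3.9). A Substudy cannot override the Master Protocol (4.1.1). This stands: only the scheduled prompt is missing.

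**Anaphylaxis is not ignored.** Section 6.2.4 ties monitoring during and after infusion to AZD8853. Its second paragraph, however, speaks of biological products generally and requires emergency drugs, equipment and trained staff. The tracer is listed among the study interventions (10.6.1.2), and 10.6.2 refers back to Section 6.2. This also stands.

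**Post-tracer vital signs.** A reader might infer that tracer recipients have no observation after the infusion, at Visit 7 or at screening, where Table 12 lists "CD8+ PET tracer administration" without linking it to vital signs. That cannot be concluded. The Visit 7 vital-signs mark is not legible in the available text. Section 8.2.3 puts vital signs before any blood draw, which implies a set on the biopsy day. The Imaging Manual, the tracer's Investigator's Brochure and the parts of Appendix I that are not visible may also require checks. In any case this question does not arise from footnote c.

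**The biopsy is also marked at V6.** Table 13 marks it there, and SAP Section 4.2.11.1 lists C2D1 tissue. The V6 safety cells are unrestricted. But C2D1 is 7 days before C2D8, outside the stated ± 5 days, so the V6 mark is itself unclear and does not close the gap at V7.

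**The restriction may be deliberate.** A lighter expansion schedule is plausible, and it is applied the same way to both rows. It makes sense at V8, where no tracer or biopsy is scheduled. No reason is given for V7.

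**Conclusion.** The point holds as a modest defect in the schedule. Footnote c removes the Part B AE/SAE and concomitant-medication prompt at V7, when up to 40 participants attend for a mandatory biopsy and up to about 20 of them for a tracer infusion. Scheduled checks are nominally 21 days apart, and the next one comes nominally 14 days after either procedure. The effect is later or less complete elicitation of non-serious events. Serious events would not be lost, and DLT assessment is untouched because it covers Part A, Cycle 1 only (10.6.8).

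The conclusion rests on the legible c in the two rows and on nominal cycle timing. It does not rest on the vital-signs mark. Whether any post-tracer observation is missing cannot be judged from the visible documents. The change is worth making but not urgent.

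**What to change.** Give the V7 cells for AE/SAE assessment and concomitant medications their own footnote, for example: *Parts A and B; in Part B, ask on the tracer day and on the biopsy day.* Keep the Part A restriction at V8. Part C is unchanged.

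The direct cost should be small: a footnote, a minor eCRF change and, by judgement, a few minutes of site time at visits already attended. Protocol amendments need ethics and regulatory approval (Appendix A 1), so the change belongs in the next planned amendment. Global Addendum 2 already anticipates one.

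Optionally, the PET footnotes of Tables 12 and 13 could cross-reference whatever post-tracer observation the Imaging Manual requires.
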